#### 8.3.1.2. Sensitivity Analyses

The analysis of time to first PE over the 52-Week treatment period is planned to be performed under the assumption that observations that are censored prior to Week 52 are censored-at-random (CAR) and that censoring is uninformative; meaning that censoring times and event times are independent. There is no plan to impute missing event times in the main analysis.

A tipping point analysis will be used as a sensitivity analysis to examine the effect of potential departures from the CAR assumption, e.g., censored-not-at-random (CNAR), in the main analysis. Due to the inherent difficulties in identifying the missing data mechanism in practice, all missing data (i.e., censoring prior to Week 52) will be assumed CNAR, and the tipping point penalties will be applied accordingly.

As the first step, an additional penalty (delta) will be applied to the assumed hazard rates for the CNAR data. For each brensocatib dose comparison relative to placebo, the tipping point penalties (delta adjustment) will be applied in a bi-directional manner. That is, the hazard rate for the CNAR data in the brensocatib arms will be incrementally increased. This worsening outlook is quantified by a sensitivity parameter  $\delta$  interpreted as an increased hazard of PE event post-dropout, while the hazard rate for the CNAR data in the placebo arm will be incrementally decreased. This process of incrementing the penalties will continue until the respective comparison is no longer statistically significant (i.e., the Tipping Point) per the multiple testing procedure described in Section 6.3 or until the unlikely incremented/decremented hazard rate has been achieved.

As the second step, MI of the missing first PE event times under the hazard rate assumptions will be implemented using Cox model. Post study withdrawal first PE event times will be imputed conditional upon hazard rate assumptions. The process of imputing the first PE missing event times will be repeated multiple times to create 100 separate data sets. If the imputed first event times are greater than 52 weeks, the participants will be censored at Week 52.

With each increment, the 100 complete data sets will each be analyzed using the same model as for the main analysis. The analysis results for each increment will be combined using Rubin's rules (Rubin 1987).

The relevant delta increment/decrement grid for each brensocatib dose comparison will be populated with the corresponding p-values. Should a Tipping Point be identified, the plausibility of the assumptions surrounding the CNAR data (i.e., magnitude of the delta adjustments in both treatment arms) will be assessed from a clinical perspective.

CONFIDENTIAL Page 58 of 139

Hazard ratios and 95% Cis for the hazard ratio corresponding to each value of  $\delta$  will be presented in a similar manner as described under the main analysis.

Technical details for the implementation in SAS can be found in Appendix I.

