# 10. STATISTICS

A detailed SAP will be developed for this study. The SAP will be finalized and approved prior to the database lock.

This study will include approximately 1620 adult subjects with NCFBE. In addition, approximately 40 adolescents will be randomized to provide an adequate description of the safety profile of brensocatib in this age group and offer the possibility to observe directional trend in terms of efficacy. In the interest of providing information to prescribers on the use of brensocatib in adult patients in a timely fashion, the planned database lock is based on the time when the targeted 1620 adult subjects (originally planned sample size) complete the 52-week treatment period or discontinue from the study before Week 52, irrespective of whether the adolescent subjects have completed the study. All adult and adolescent data collected up to this database lock will be included in the primary efficacy and safety analyses for the CSR. Additional data collected between database lock and the last adolescent subject completing the last visit will be summarized in a CSR addendum. Any additional analyses of efficacy and safety data will be detailed in the SAP.

All of the efficacy and safety data that have already been collected from 44 Ukraine subjects impacted by the war in Ukraine will be listed only and not included in the formal efficacy and safety analyses, as agreed with FDA and EMA.

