## Participant's Follow-up Time or Observation Time

The individual follow-up time / observation time in years will be calculated using the following formula:

$$follow - up \ time \ (years) = \frac{date \ of \ EOS - date \ of \ first \ IP \ intake}{365.25}$$
.

For participants ongoing at time of primary analysis, e.g., adolescents, the date of cut-off will be used as date of EOS.

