#### 8.3.3.2. Sensitivity Analyses

A tipping point analysis will be used to investigate the impact of missing data and to examine the robustness of the main analysis. The tipping point will be identified when the respective comparison is no longer statistically significant at two-sided  $\alpha$ = 0.05.

To explore the impact of missing data on the mean treatment effect, different assumptions of the effect will be evaluated by adding an additional penalty (delta) prior to analyzing the imputed datasets and combining the results. For each brensocatib dose comparison relative to placebo, the tipping point penalties (delta adjustment) will be applied in a bi-directional manner. The deltas or delta adjustments are pre-selected multiples of the observed treatment effect. If the observed mean treatment effect from the main analysis is x, the deltas to be investigated will range from -3\*x to 0 for the active arm, in increments of 10 mL. The delta adjustments to be applied to the imputed data in placebo arm will range from 0 to 3\*x. The increment or range may be refined based on the analysis results and the location of the tipping point.

All recorded data up to and including the Week 52 assessment (see Section 2) will be included. Missing data will be imputed using multiple imputation first based on the MAR mechanism. The imputation model will contain the same covariates as in the main analysis model (see Section 8.3.3.1). 100 separate complete data sets for each comparison within the pre-selected delta range will be generated and analyzed. Markov Chain Monte Carlo (MCMC) method will be used to fill intermittent missing values, e.g., missing values between reported visits, under the assumption of MAR, resulting in an intermediate data with monotone missing patterns. MCMC will use a separate chain for each imputation (multiple chains), a non-informative prior for the means and covariances, and 200 burn-in iterations before the very first imputation in each chain. For monotone missing data the regression method will be applied using a separate regression for each of the non-monotone imputed datasets. Results will be combined across imputations using Rubin's method (Rubin 1987). The relevant delta decrement grid for each brensocatib dose vs. placebo comparison will be populated with the corresponding p-value.

Technical details for the implementation in SAS can be found in Appendix I.

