# Primary Endpoint: Annualized Rate of Pulmonary Exacerbations—Tipping Point (Sensitivity Analysis)

Participants may discontinue from the study prior to the end of the 52 weeks treatment period, so that the number of PEs after discontinuation is unknown. Table 19 splits the number of events and participants time at risk into two periods, the observed period (Period 1), and the unknown period (Period 2). According to Section 6.7.1 a participant will not be at risk in the days from the start to the end of a PE. Therefore, the sum of periods T1 and T2 might be smaller than the protocol specified treatment period of 52 weeks.

Table 19: Differentiation of Events and Duration for Participants with missing Followup Time

Period:	Period 1	Period 2	Total (52 weeks)
Status:	Patient is on-study	Patient is off study	
Status.	(PEs are observed)	(PEs not observed)	

CONFIDENTIAL Page 112 of 139

Duration (years) followed:	T1	T2	T = T1 + T2
Number of PEs within the period:	$Y_1, Y_{obs}$	$Y_2, Y_{mis}$	Y = Y1 + Y2

T1 and Y1 are known, T2 and Y2 are unknown. T will be set to 1 for participants who discontinue from the study early..

T1>0, T2\ge 0. If T2=0, then Y2=0 and there is no missing data for the corresponding participant.

$$T2 = 1 - T1$$

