#### PROC SQL;

```
PROC SORT DATA=tte5 (RENAME=(ttpe=pred_ttpe)) OUT=tte6;
BY trtn region1 psaecol numpes agegr3 usubjid n_surv DESCENDING p_surv;
RUN;
```

```
DATA tte7;
   SET tte6;
   BY trtn region1 psaecol numpes agegr3 usubjid n_surv DESCENDING p_surv;
   IF LAST.usubjid THEN OUTPUT;
RUN;
```

The variable pred\_ttpe is the new predicted Time to Pulmonary Exacerbation event.

Step 4: Using the original tte dataset, replace any participants censored prior to Week 52 as identified using ttpe and cnsr, with the pred\_ttpe from the above process, updating their censoring flag to be an event. Note: this will create 100 datasets separately for each delta tipping point. Each of the datasets will be analyzed using a cox proportional hazards model outputting the parameter estimate and standard error for the trtn (Active vs Placebo) comparison (for example - into pe1 to pe100).

CONFIDENTIAL Page 120 of 139

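### The time-to-first-PE tipping point penalises all censoring before Week 52, so participants still ongoing at the primary lock, mainly adolescents, are treated as dropouts

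*SAP*

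**What the plan says.** **Time to first PE.** SAP 8.3.1.2 states that "all missing data (i.e., censoring prior to Week 52) will be assumed CNAR, and the tipping point penalties will be applied accordingly". The penalty runs in both directions: "the hazard rate for the CNAR data in the brensocatib arms will be incrementally increased", while "the hazard rate for the CNAR data in the placebo arm will be incrementally decreased". Appendix I, Step 4 of this tipping point, tells the programmer to "replace any participants censored prior to Week 52 as identified using ttpe and cnsr". Those two variables hold the time and the censoring flag. Neither carries the reason for censoring.

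**Who is ongoing at the lock.** Protocol section 10 sets the database lock by the 1620 adults, "irrespective of whether the adolescent subjects have completed the study". SAP 4.2 includes adult and adolescent data collected up to that lock in the primary analyses. SAP 6.4.7 says: "For participants ongoing at time of primary analysis, e.g., adolescents, the date of cut-off will be used as date of EOS". SAP 6.7.1 has a similar cut-off rule for PE end dates, and SAP 7.1 plans a disposition count of participants ongoing at the lock.

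**FEV1 and QoL-B.** SAP 8.3.3.2 says: "Missing data will be imputed using multiple imputation first based on the MAR mechanism". In Appendix I, Step 3, the MNAR ADJUST statements then shift the imputed values, choosing observations by treatment arm only. SAP 8.3.5.2 carries the method over to QoL-B, which is adults only.

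**Primary endpoint.** SAP 8.2.2 also declares all missing data to be MNAR, but its imputation steps concern the time after study discontinuation. Appendix I adds: "T will be set to 1 for participants who discontinue from the study early".

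**The concern.** SAP 8.3.1.2 justifies the not-at-random assumption by the difficulty of knowing why data are missing. For a participant who is PE-free and still in the study at the lock, the reason is known: follow-up was cut by the calendar. The same section describes delta as a raised hazard after dropout and speaks of imputing event times after withdrawal. An ongoing adolescent has done neither, so the selection rule is wider than the quantity it is meant to vary.

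What is at stake is the interpretation of the tipping delta. SAP 8.3.1.2 asks for the deltas at the tipping point to be judged for clinical plausibility, which is a judgement about outcomes after dropout. A delta that also depends on when adolescents happened to enrol cannot be read that way. Because adolescents are allocated 2:2:1, the extra penalised cases are also expected to fall unevenly, with more in each active arm than on placebo.

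**Working it through.** **1. Allocation (reproduces the plan).** About 40 adolescents at 2:2:1 (SAP 3.2): 40 × 2/5 = 16, 40 × 2/5 = 16, 40 × 1/5 = 8. With 540 adults per arm, the ceiling on affected adolescents is 16/(540+16) = 2.9% of an active arm, 8/(540+8) = 1.5% of placebo, and 40/1660 = 2.4% overall.

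**2. Planning inputs.** Protocol 10.1 gives a placebo rate of 1.2 per year, dispersion 1 and rate ratio 0.70, hence 0.84 on active. As a check, Var(log RR) = [(1/1.2 + 1) + (1/0.84 + 1)]/540 = 0.00745. Power at two-sided 0.005 is then 0.907, against the stated 90%.

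**3. Who would be penalised.** A participant must also be PE-free at the cut-off. With dispersion 1, P(PE-free at t years) = 1/(1 + rate × t). If all adolescents were cut at t:

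| t (years) | Active, 16/(1+0.84t) | Placebo, 8/(1+1.2t) | Ratio |
|---|---|---|---|
| 0.25 | 13.2 | 6.2 | 2.15 |
| 0.50 | 11.3 | 5.0 | 2.25 |
| 0.75 | 9.8 | 4.2 | 2.33 |

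So about 2:1 or slightly more is expected. This is an expectation, not a known count.

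**4. Growth of the penalised set (upper bound).** Assume 10% adult dropout (54 per arm), all adolescents ongoing, and both groups' follow-up uniform over the year. The PE-free fraction is ln(1 + rate)/rate: 0.726 on active and 0.657 on placebo. Active grows from 54 × 0.726 = 39.2 by 16 × 0.726 = 11.6, or 30%. Placebo grows from 54 × 0.657 = 35.5 by 8 × 0.657 = 5.3, or 15%.

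**5. Effect on the test (upper bound).** One dose against placebo was simulated in 500 trials, with 540 adults per arm plus 16 and 8 adolescents, the planning rates, all adolescents ongoing, and follow-up uniform over 0 to 52 weeks. Censored times were imputed under S(t) raised to the power delta, as in Appendix I. The simulation is simplified: there are no covariates, the true survival curve is used, and there is one imputation per trial. Mean Cox z:

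| Adult dropout | Delta active / placebo | Ongoing adolescents penalised | Ongoing adolescents censored only | Shift |
|---|---|---|---|---|
| 5% | 2 / 0.5 | -2.64 | -2.78 | 0.14 |
| 5% | 3 / 0.33 | -2.37 | -2.60 | 0.23 |
| 10% | 2 / 0.5 | -2.39 | -2.53 | 0.13 |
| 10% | 3 / 0.33 | -1.96 | -2.18 | 0.22 |
| 15% | 2 / 0.5 | -1.98 | -2.11 | 0.13 |
| 15% | 3 / 0.33 | -1.37 | -1.59 | 0.22 |

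At delta 1 the two columns differ by 0.01 or less. A separate run of 400 trials, with 12% dropout, ratio 0.72 and delta 3 on active with 1/3 on placebo, gave shifts of 0.11 with half of the adolescents ongoing and 0.16 with three quarters ongoing.

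I do not convert these shifts into a change in the tipping delta. The between-trial SD of z is about 0.9, so the delta at which an average z crosses a threshold moves with simulation noise and with the assumed inputs. The paired shift is stable; the crossing point is not.

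**The case against.** The best defence is that dropouts are plainly the intended target. SAP 8.3.1.2 uses dropout and withdrawal language, and a sensible programmer might exclude ongoing participants unprompted. That stands as evidence of intent. It does not change the stated selection rule, which has no exception and is repeated in Appendix I, Step 4.

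A reader might infer that the plan handles the primary endpoint correctly and the secondary ones wrongly. That is too strong. SAP 8.2.2 carries the same blanket sentence. The difference is only that its imputation steps are written for study discontinuers, whereas Step 4 for time to first PE and Step 3 for FEV1 are not.

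A reader might also infer that twice as many active as placebo adolescents will be penalised. The documents give the planned allocation, not the number unfinished at the lock, which could be close to zero.

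It is also fair that cut-off censoring for this endpoint is inferred. SAP 6.4.7 sets the cut-off as the EOS date for follow-up time. SAP 6.7.1.6, which governs time to first PE, names only Week 52 and early study discontinuation. The inference is reasonable, and the silence is a gap to close.

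Finally, under SAP 6.2 the tipping point runs only after a significant main result, and the direction is against brensocatib. SAP 8.3.6 repeats the main secondary analyses in adults alone. All of this limits the consequence. However, the adult repeat covers the main analysis and not the tipping point, and a conservative delta is still not one that describes dropouts.

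**Conclusion.** The concern holds as a fault in a sensitivity analysis. Followed literally, the plan penalises administrative censoring in the time-to-first-PE tipping point. It also shifts the unreached visits of ongoing participants in the FEV1 tipping point and, for any adults still ongoing, in QoL-B.

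The effect is small and conservative: about 0.1 to 0.2 in z at delta 2 to 3. That rests on the planning rates, on assumed adult dropout of 5% to 15%, and for the larger values on every adolescent being ongoing. No corresponding effect was computed for FEV1 or QoL-B.

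It would be wrong to conclude that the secondary-endpoint inference is biased. The main Cox model leaves these participants censored without penalty, so the tests of H3 and H4 and the other alpha-controlled decisions do not change.

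**What to change.** - **SAP 8.3.1.2 and Appendix I, Step 4 (time to first PE):** apply delta only to participants who discontinued the study before Week 52. Keep participants ongoing at the data cut-off censored at the cut-off, under the censored-at-random assumption of the main analysis.
- **SAP 8.3.3.2 and Appendix I, Step 3 (FEV1, and QoL-B through 8.3.5.2):** impute the unreached visits of ongoing participants under MAR with zero delta.
- **SAP 6.7.1.6:** state the cut-off date as the censoring date for PE-free participants ongoing at the primary lock.

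The cost is a few sentences before lock and unblinding, plus one ongoing-at-cut-off flag in the tipping-point programs. The flag can be derived from the disposition category already planned in SAP 7.1. No new data are needed and no main analysis changes.

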#### 8.3.1.3. Supplementary Analyses

The supplementary Estimand for the time to first PE over the 52-Week treatment period is the On-IP Estimand (see Section 2) and will utilize the ITT Analysis Set (see Section 5.2). The time-to-event model of the main analysis will be implemented for this Estimand (see Section 8.3.1.1). Participants who do not have an event during the 52-Week treatment period will be censored at the day of last treatment administration.

#### 8.3.2. Responder Status for Exacerbation-Free over the 52-Week Treatment Period

#### 8.3.2.1. Main Analyses

The Estimand of the responder status for exacerbation-free over the 52-week treatment period is the On-Study Estimand in which all observed data will be included in the analysis (see Section 2). The ITT Analysis Set (see Section 5.2) will be used for this Estimand. The derivation of the endpoint is detailed in Section 6.7.2.

The number and percentage of Responders/Non-responders over the 52-Week Treatment Period will be presented by treatment group.

Responder status at Week 52 will be compared between treatment groups brensocatib vs. placebo using a logistic regression model including treatment group, sputum sample being classified as positive or negative for *Pseudomonas aeruginosa* at Screening Visit, the number of prior PEs [<3 or ≥3] in the previous 12 months, stratification region (North America, Europe, Japan, and the Rest of the World), and age group (adult, adolescent) as fixed effects. If the age group covariate creates estimability issues, it may be removed. An estimate of the odds ratio for the treatment comparison (brensocatib 10mg vs. placebo; brensocatib 25mg vs. placebo) and the 95% Wald confidence interval will be summarized; the corresponding p-value from the Wald chi-square test will be compared to the appropriate alpha level per the multiple test procedure.

For participants who discontinue the study prior to Week 52 without having experienced a PE confirmed through adjudication, their responder status will be missing. To address this issue, first event times for these participants will be imputed based on the observed data model for the time period after discontinuation from the trial. If the imputed event time occurs prior to Week 52, the participant will be considered a non-responder. Otherwise, the participant will be considered a responder. The process of imputing missing PE data will be repeated multiple times to create 100 separate datasets. With each increment, the 100 complete data sets will each be analyzed using the logistic regression model described above. The analysis results will then be combined using Rubin's rules (Rubin 1987).

Technical details for the implementation in SAS can be found in Appendix I.

CONFIDENTIAL Page 59 of 139

